## 1. PROTOCOL SUMMARY

Title: Brain-Gut Axis Regulatory Mechanism of Anxiety and Depression in Irritable Bowel Syndrome

Study Design: Prospective, observational, case-control study

Study Duration: April 2025 – April 2026

Study Sites: Air Force Medical University, Second Affiliated Hospital (Tangdu Hospital)

Population: 100 IBS patients and 100 healthy controls (HC), aged 18–60 years

Primary Objective: To investigate the brain-gut axis regulatory mechanisms underlying anxiety and depression in IBS using 7T multimodal MRI, metagenomics, and metabolomics.

Key Assessments:

7T MRI: Structural (3D-T1WI), functional (resting-state fMRI), diffusion (DWI/DTI), and metabolic (ASL) imaging

Clinical: Rome IV criteria, symptom scores, Bristol Stool Scale

Psychological: Beck Anxiety Inventory (BAI), Beck Depression Inventory (BDI), Pittsburgh Sleep Quality Index (PSQI), cognitive assessments

Biological: Fecal metagenomic sequencing, serum and fecal metabolomics

## 2. BACKGROUND AND RATIONALE

### 2.1 Study Background

Irritable Bowel Syndrome (IBS) is a common functional gastrointestinal disorder characterized by recurrent abdominal pain and altered bowel habits, with a global prevalence of approximately 4.8%. IBS significantly impairs quality of life and imposes substantial economic burden—estimated annual direct and indirect costs in China exceed 123 billion RMB.

Anxiety and depression are frequent comorbidities in IBS. Approximately 50% of IBS patients meet diagnostic criteria for mood disorders, and in two-thirds of comorbid cases, IBS diagnosis precedes the onset of mood disorders. This temporal sequence suggests that gut-brain axis (GBA) dysfunction plays a central role in the pathophysiology of both IBS and its psychiatric comorbidities.

The gut-brain axis is a bidirectional communication network integrating endocrine, immune, neural, and microbial signals. Gut microbiota influence host physiology through metabolites such as short-chain fatty acids (SCFAs), bile acids, and tryptophan derivatives. IBS patients exhibit

characteristic microbiome alterations, including increased Firmicutes, decreased Bacteroidetes, and reduced abundance of beneficial genera such as *Bifidobacterium* and *Faecalibacterium*. These alterations may regulate intestinal permeability, visceral sensitivity, and neuroinflammation through metabolites (e.g., histamine, bile acids), thereby triggering anxiety and depression.

However, current studies are limited by sampling techniques and in vivo brain functional research methodologies, making it difficult to elucidate the molecular mechanisms of anxiety and depression in IBS. Ultra-high-field 7T MRI offers submillimeter resolution and multimodal imaging capabilities (structural, functional, and metabolic), enabling precise capture of brain functional network reorganization. Combined with metagenomics and metabolomics, this study aims to decode the gut microbiota–metabolite–brain functional network associations in IBS patients, providing evidence for targeted therapy and rapid diagnosis.

## 2.2 Rationale

### Biological Basis of IBS-Anxiety/Depression Comorbidity

Gut microbiota influence the central nervous system directly or indirectly through metabolites such as secondary bile acids and tryptamine. For example, tryptamine activates 5-HT receptors to regulate intestinal secretion, while secondary bile acids (e.g.,  $\alpha$ -MCA, HDCA) inhibit TH17 cell differentiation via TGR5 receptors, attenuating intestinal inflammation. Key brain regions in IBS patients (e.g., amygdala, anterior cingulate cortex) show reduced gray matter volume and altered resting-state functional connectivity, overlapping with neural circuits implicated in anxiety and depression. Genome-wide association studies have identified shared genetic risk loci between IBS and anxiety/depression (e.g., 5-HT transporter gene polymorphisms), suggesting common pathophysiological mechanisms.

### Technical Advantages of 7T MRI

7T MRI 3D-T1-weighted imaging can identify neuronal microstructural changes at submillimeter resolution. Diffusion-weighted imaging (DWI) reduces fiber tracking error rates by 40% compared to 3T, enabling clearer visualization of fine fiber projections. Resting-state fMRI reveals functional connectivity abnormalities, while arterial spin labeling (ASL) assesses cerebral hemodynamics. Integration of these neuroimaging modalities with metabolomics data enables construction of a comprehensive brain-gut axis regulatory atlas.

## 3. STUDY OBJECTIVES

#### Primary Objective:

To investigate the brain-gut axis regulatory mechanisms of anxiety and depression in IBS by integrating 7T multimodal MRI, fecal metagenomics, and metabolomics.

#### Secondary Objectives:

To identify key gut microbiota and metabolite signatures associated with brain functional reorganization in IBS patients with anxiety/depression.

To construct a brain-gut axis regulatory atlas using 7T MRI multimodal imaging.

To discover potential probiotic/prebiotic targets and rapid diagnostic biomarkers for IBS with psychiatric comorbidities.

#### Scientific Hypothesis:

IBS-related anxiety and depression are mediated by specific gut microbiota-metabolite profiles that modulate brain functional networks via the gut-brain axis, and these alterations can be captured by 7T multimodal MRI and multi-omics approaches.

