## 4. STUDY DESIGN AND METHODS

### 4.1 Study Design

This is a prospective, observational, case-control study conducted at Air Force Medical University, Second Affiliated Hospital.

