### 6.2 Follow-up Schedule

#### Baseline (Enrollment):

Complete clinical assessment, psychological scales, MRI scan, fecal/blood sample collection

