#### 3-Month Follow-up (IBS Group Only):

Repeat anxiety/depression scales

Repeat fecal/blood sample collection

Assess symptom relief (abdominal pain frequency, stool characteristics)

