#### 6-Month Follow-up (Optional):

Long-term efficacy tracking

Repeat imaging data collection (selected patients)

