### 7.2 Statistical Analysis

Group comparisons: Independent t-test (normal distribution) or Mann-Whitney U test (non-normal)

Correlation analysis: Pearson or Spearman correlation coefficients

Multi-omics integration: Sparse Canonical Correlation Analysis (sCCA), Principal Component Analysis (PCA)

Machine learning: Random Forest for key biomarker selection; ROC curve for diagnostic efficacy evaluation

Covariate adjustment: Age, sex, BMI, and other confounders in multivariate regression models

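### The hypothesis claims directional mediation from gut to brain to mood, but the visit schedule and the methods named in Section 7.2 can support association only

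*Protocol*

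**What the plan says.** - **Hypothesis (Protocol Section 3).** "IBS-related anxiety and depression are mediated by specific gut microbiota-metabolite profiles that modulate brain functional networks via the gut-brain axis". The primary objective likewise speaks of regulatory mechanisms. The first secondary objective and the closing aim of Section 2.1 use the language of association.
- **Design (Section 4.1).** "This is a prospective, observational, case-control study". No study treatment is described.
- **Baseline (Section 6.2).** "Complete clinical assessment, psychological scales, MRI scan, fecal/blood sample collection", all at enrolment.
- **3 months (Section 6.2), IBS group only.** "Repeat anxiety/depression scales" and "Repeat fecal/blood sample collection", plus symptom relief. No MRI is listed.
- **6 months (Section 6.2), optional.** "Long-term efficacy tracking", with imaging repeated in selected patients. The number of patients and the selection rule are not given, and neither scales nor samples are named.
- **Analysis (Section 7.2).** Group tests (t-test or Mann-Whitney), "Correlation analysis: Pearson or Spearman correlation coefficients", sCCA and PCA, Random Forest with ROC curves, and multivariate regression adjusted for age, sex, BMI and other confounders.
- **Sample size (Section 5).** A two-sample comparison of means with a difference of 0.5 and SD 1.0, two-sided 5%, 80% power: 64 per group, 20% dropout, target 100 per group.

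**The concern.** The hypothesis gives an order: gut profile first, brain network second, mood third. Correlation and sCCA are symmetric, so they fit mood acting on the gut as well as the gut acting on mood. Regression on same-visit data takes its direction from the analyst, not from the data. Section 2.1 itself describes the gut-brain axis as bidirectional, so the reverse order is a live alternative.

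The 3-month scales and samples are the one full-group source of time order, yet the protocol's analysis section names no method for them. If the plan is followed as written, a set of same-visit associations could be read as confirming the mediation hypothesis.

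Two smaller matters belong with this. Section 7.2 does not say whether gut-brain correlations are run within group or on patients and controls together, and pooling can produce a correlation from group differences alone. The 6-month visit is also labelled as tracking efficacy in a study that describes no treatment.

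**Working it through.** **1. The plan's own figure.** n = 2 × (1.960 + 0.842)² × 1.0² / 0.5² = 62.8, so 63 per group. The t-based solution is 63.77, so 64, and the stated figure reproduces. Dropout: 64 / 0.8 = 80; the target of 100 is above that. This sizes an IBS-versus-control mean difference (power 0.94 at 100 and 0.89 at 80 per group). It does not size an indirect effect within IBS.

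**2. When each domain is measured.**

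| Visit | Gut | Brain (MRI) | Mood |
|---|---|---|---|
| Baseline | yes | yes | yes |
| 3 months, IBS only | yes | not listed | yes |
| 6 months, optional | not listed | selected patients | not listed |

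Only baseline has all three. The 6-month imaging does not fill the gap: the subset is undefined and no gut or mood measurement is named beside it.

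**3. Same-visit data cannot give the order.** Take standardised paths a (gut-brain) and b (brain-mood) with no direct gut-mood link. Then corr(gut, brain) = a, corr(brain, mood) = b and corr(gut, mood) = a × b, whichever end the chain starts from. With a = b = 0.3 the three correlations are 0.30, 0.30 and 0.09 under both orders.

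Simulation of a joint-significance test (gut-brain path, and brain-mood path given gut; 4,000 runs per setting; path sizes are assumptions) gives this share of positive results:

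| IBS patients | Paths | True order gut-brain-mood | True order mood-brain-gut |
|---|---|---|---|
| 100 | 0.2 | 0.25 | 0.25 |
| 100 | 0.3 | 0.73 | 0.72 |
| 100 | 0.4 | 0.96 | 0.95 |
| 80 | 0.2 | 0.18 | 0.18 |
| 80 | 0.3 | 0.57 | 0.58 |
| 80 | 0.4 | 0.90 | 0.91 |

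The two orders agree within simulation error.

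**4. Pooling, if it is done.** Suppose two variables are unrelated within each group, but both differ by d SD between two equal groups. Pooled r = (d²/4) / (1 + d²/4). At the protocol's own d = 0.5 this is 0.0625 / 1.0625 = 0.059. The two-sided 5% critical value at N = 200 is 0.139, so the expected r is below it, but the error rate still rises. By Fisher's z, 0.059 × √197 = 0.83, and P(Z > 1.96 − 0.83) + P(Z < −1.96 − 0.83) = 0.13. Simulation (40,000 runs) also gives 13%. At d = 0.8 and 1.0, pooled r is 0.138 and 0.200, with false-positive rates of about 50% and 83%. Adjusting for group returns the rate to 5%.

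**5. Power of a lagged within-IBS model.** With 80 of 100 patients left after 20% dropout, the detectable correlation at 80% power is tanh(2.802 / √77) = 0.309. With five covariates it is tanh(2.802 / √72) = 0.319. This is for one coefficient. The joint test of two paths of 0.3 has power of about 0.57 at n = 80 (table above, same-visit illustration).

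**The case against.** The strongest reply is that the protocol promises less than the hypothesis sentence suggests. The primary objective is to investigate, the first secondary objective and Section 2.1 speak of associations, the design is called observational, and Section 8.1 commits to STROBE reporting. Nothing states that mediation will be declared from a correlation. This stands in part: the inconsistency lies between the hypothesis and the rest of the document, and wording can remove most of it.

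A second reply is that a longitudinal or mediation model may be in a statistical analysis plan that is not shown, and that the regression line in Section 7.2 could hold one. This also stands. A reader might infer that the 3-month data will go unused; the documents support only that this protocol names no analysis of them. But an analysis plan cannot add a 3-month MRI or change the wording of the hypothesis.

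Other stronger readings also fail:

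- A reader might say that only correlation and sCCA are planned. Section 7.2 lists group tests, PCA, Random Forest with ROC and adjusted regression as well, though none is described as a mediation or repeated-measures analysis.
- A reader might take pooled correlations as planned. The protocol does not say so, and the first secondary objective points to IBS patients. The pooling figures are conditional.
- A reader might expect follow-up change to be largely regression to the mean. The inclusion criteria set no anxiety or depression threshold, so selection on high scores is not shown, and the documents give no retest correlation from which to size it.

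**Conclusion.** The point holds in this form: the hypothesis asserts directional mediation, and the schedule together with the methods named in the protocol can support association only. That rests on reading the sections side by side and needs no assumed number. The simulation shows the size of the ambiguity (0.73 against 0.72 at n = 100) on assumed paths of 0.3 and complete data; the equality of the two orders does not depend on the path size chosen.

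The pooling risk is real but conditional: a false-positive rate of about 13% instead of 5% if groups are pooled without adjustment and both variables shift by 0.5 SD. The efficacy label is a wording fault, because no study treatment is described.

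No participant safety issue arises. What is at stake is whether the headline conclusion goes beyond the design.

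**What to change.** 1. **Hypothesis and planned conclusions.** Word them as association, in line with Section 2.1 and the first secondary objective.
2. **Section 7.2, lagged model.** Within the IBS group, regress 3-month BAI and BDI on the baseline microbial or metabolite score and the baseline imaging measure, adjusted for the baseline value of the same scale, age, sex and BMI. Use Module 6 medication use only in a sensitivity analysis: it is recorded after baseline, and adjusting for it may block or bias the effect.
3. **Indirect effect.** If estimated, report it with a bootstrap interval as exploratory, and state that gut and brain are still measured at the same visit. The lagged model puts both before 3-month mood but does not order them relative to each other.
4. **Gut-brain correlations and sCCA.** Run them within the IBS group or adjusted for group.
5. **6-month visit.** Replace the efficacy label with symptom course.

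Cost: protocol wording and analysis time, with no new visit, scan or sample. The claim becomes more modest and power is limited: about 80% for a single partial correlation of 0.31 to 0.32 in 80 patients, and lower for an indirect effect (about 0.57 if both paths are 0.3). If mood changes little over 3 months, adjustment for baseline will leave less to explain and power will be lower still.

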## 4. STUDY DESIGN AND METHODS

### 4.1 Study Design

This is a prospective, observational, case-control study conducted at Air Force Medical University, Second Affiliated Hospital.

### 4.2 Study Population

#### Inclusion Criteria – IBS Group:

Right-handed, aged 18–60 years, education  $\geq 6$  years

Meets Rome IV diagnostic criteria for IBS:

Symptom onset  $\geq 6$  months prior to diagnosis

Recurrent abdominal pain  $\geq 3$  days/month in the last 3 months, plus  $\geq 2$  of:

- a. Improvement with defecation
- b. Onset associated with change in stool frequency
- c. Onset associated with change in stool form (appearance)

Supporting symptoms: abnormal stool frequency ( $<3$ /week or  $>3$ /day), abnormal stool form (Bristol Types 1–2 or 6–7), straining, urgency, incomplete evacuation, mucus in stool, or bloating

#### Exclusion Criteria – IBS Group:

History of anti-anxiety/depressant medication (SSRIs/SNRIs, Chinese patent medicines, etc.)

within the past month

History of antibiotics or probiotics use within the past month

Inflammatory bowel disease (IBD), intestinal obstruction, other gastrointestinal diseases, or gastrointestinal surgery

Current or past psychiatric or neurological disorders (e.g., psychosis, brain tumors, consciousness disorders)

Severe hepatic/renal insufficiency, cardiovascular/cerebrovascular disease, or malignancy

Contraindications to 7.0T MRI:

Ferromagnetic implants (cardiac pacemaker, defibrillator, neurostimulator, aneurysm clip, cochlear implant, or any metallic foreign body)

Non-ferromagnetic implants (e.g., titanium alloy, orthopedic implants), intrauterine devices, non-removable dentures (including implants)

Metal foreign bodies in eyes or body (metal fragments, shrapnel, metal shavings), history of welding work or metallic foreign body injury

Tattoos or permanent makeup (eyebrows, lips) within the last month

Claustrophobia

Fever

Inclusion Criteria – Healthy Control (HC) Group:

Right-handed, aged 18–60 years, education  $\geq 6$  years

All physiological indices within normal range, no disease manifestations

No family history of psychiatric or neurological disorders

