#### Module 3: Psychological Evaluation

Auditory Verbal Learning Test, Color Test, Montreal Cognitive Assessment (MoCA), Memory Span Test, Beck Anxiety Inventory (BAI), Beck Depression Inventory (BDI), Pittsburgh Sleep Quality Index (PSQI)

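### The IBS exclusion of any current or past psychiatric disorder has no exception for anxiety or depressive disorders, so as written it conflicts with the secondary objectives and narrows the primary one

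*Protocol*

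**What the plan says.** **Eligibility.** Protocol section 4.2, exclusion criteria for the IBS group, excludes "Current or past psychiatric or neurological disorders (e.g., psychosis, brain tumors, consciousness disorders". No severity limit is given, and anxiety and depressive disorders are not excepted. The same list has a separate drug exclusion, "History of anti-anxiety/depressant medication (SSRIs/SNRIs, Chinese patent medicines, etc", which applies only to use within the past month. Section 8.1 relies on strict application of the criteria, with consecutive enrolment, to control selection bias.

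**Objectives.** The primary objective in section 3 is "To investigate the brain-gut axis regulatory mechanisms of anxiety and depression in IBS by integrating 7T multimodal MRI, fecal metagenomics, and metabolomics". The secondary objectives look for microbial and metabolite signatures "associated with brain functional reorganization in IBS patients with anxiety/depression" and for "rapid diagnostic biomarkers for IBS with psychiatric comorbidities".

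**Rationale.** Section 2.1 states: "Approximately 50% of IBS patients meet diagnostic criteria for mood disorders".

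**Measurement.** Section 6.1, Module 3, lists "Beck Anxiety Inventory (BAI), Beck Depression Inventory (BDI), Pittsburgh Sleep Quality Index (PSQI" among the psychological tests. Section 6.2 collects the scales, MRI and samples at baseline and repeats the anxiety and depression scales in the IBS group at 3 months. The protocol sets no BAI or BDI cut-off for entry and lists no diagnostic interview.

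**The concern.** A psychiatric comorbidity is a psychiatric disorder. An exclusion covering every current or past psychiatric disorder therefore removes the patients whom a secondary objective names. The examples in the criterion illustrate the class but do not limit it, and nothing else in the protocol tells a recruiter that anxiety and depressive disorders are exempt. The word for past disorders also removes patients in remission.

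Three things are at stake:

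- Biomarkers meant for IBS with psychiatric comorbidity would be developed in a sample from which identified comorbidity had been removed.
- BAI and BDI scores would tend to be thinned at the upper end, which weakens their correlations with brain and gut measures.
- Two recruiters who read the criterion differently would enrol different populations.

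No later analysis plan can repair this, because it cannot analyse patients who were never enrolled.

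**Working it through.** **1. The passages side by side**

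| Place in protocol | Who is meant |
|---|---|
| 2.1 Study Background | IBS patients, about half meeting criteria for a mood disorder |
| 3, primary objective | Anxiety and depression in IBS; no diagnosis required |
| 3, secondary objectives | IBS patients with anxiety/depression; IBS with psychiatric comorbidity |
| 4.2, IBS exclusions | No current or past psychiatric disorder of any kind |

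Row 4 read literally is incompatible with row 3. It is compatible with row 2 only for symptoms without an identified diagnosis.

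**2. The plan's own sample size**

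Section 5 gives δ = 0.5, σ = 1.0, two-sided α = 0.05 and power 80%. The formula gives 2 × (1.960 + 0.842)² / 0.5² = 62.8, so 63 per group; the t-based calculation gives 64. The stated 64 is reproduced. It sizes an IBS-versus-control comparison of means, so it does not bear on the conflict. The target of 100 IBS patients less 20% dropout leaves 80, which is used below.

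**3. Share of patients affected**

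If everyone who meets criteria were identified and turned away, enrolling 100 would take 100 / (1 − 0.50) = 200 otherwise eligible patients. For an assumed share of 30% to 60% the figure is 143 to 250. The 50% refers to mood disorders only. These numbers apply only if screening detects every case, which the protocol does not show.

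**4. Illustration of the range restriction**

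Assumptions, none of them in the documents:

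- The true correlation between mood score and a brain or gut measure is 0.30.
- Score and diagnostic liability are normal, and the upper 50% of liability is excluded.
- Liability correlates ρ with the score and relates to the brain or gut measure only through it.

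Removing the upper half of a standard normal leaves variance 1 − 2/π = 0.363. The score variance becomes k² = 1 − ρ²(1 − 0.363). The correlation becomes r′ = 0.30k / √(1 − 0.09 + 0.09k²). Power uses Fisher's z: Φ(√(n − 3) × atanh r′ − 1.96), two-sided 0.05.

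| ρ | k (score SD) | r′ | Power, n = 80 | Power, n = 100 |
|---|---|---|---|---|
| No exclusion | 1.00 | 0.30 | 78% | 86% |
| 0.5 | 0.92 | 0.28 | 70% | 80% |
| 0.7 | 0.83 | 0.25 | 62% | 72% |
| 1.0 (worst case) | 0.60 | 0.19 | 38% | 46% |

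Worst case at n = 80: r′ = 0.30 × 0.603 / √(0.91 + 0.09 × 0.363) = 0.186; √77 × 0.1885 = 1.654; 1.654 − 1.960 = −0.306; Φ = 0.380.

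If only the upper 30% is removed with ρ = 1, k = 0.70, r′ = 0.22 and power at n = 80 is 48%.

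**The case against.** A reader might infer that the study cannot answer its own question, or that only patients below the diagnostic threshold could enter. The documents support neither reading, for these reasons:

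- The primary objective speaks of anxiety and depression, not of diagnosed disorders. BAI and BDI measure symptoms without a cut-off, so patients with symptoms but no identified diagnosis still serve it. **This stands:** the objective is narrowed, not lost.
- No diagnostic interview is listed, and the psychiatric evaluation mentioned in section 8.1 is not described. If screening relies on known history, patients who meet criteria but are undiagnosed can enter with high scores. **This stands.** It also means that half of the source population is not shown to be ineligible.
- The examples in the criterion are severe or organic conditions, and a one-month limit on anti-anxiety and antidepressant drugs would be largely redundant if any past anxiety or depressive disorder already excluded. The sponsor may have meant to admit these patients. **This makes the narrower reading plausible, but it does not rescue the wording,** since the criterion would then not say what was meant.
- The 38% is an extreme. Past disorders need not score high now, and BAI, BDI, MRI and samples are all collected at baseline, so follow-up dropout need not reduce the sample to 80. Nor is this a loss of planned power, because section 5 sizes a different comparison. **This stands,** and the figures serve as illustration only.

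**Conclusion.** The textual conflict is firm. Applied as written, the exclusion contradicts the secondary objectives on IBS with anxiety/depression and with psychiatric comorbidity, and it undercuts the rationale in section 2.1. The primary objective survives, but it is confined to symptoms without an identified diagnosis and to a restricted score range.

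The size of the loss is uncertain. Under the stated assumptions, power for a correlation of 0.30 with 80 patients falls from 78% to between 62% and 70% when diagnosis and score correlate 0.7 to 0.5, and to 38% only if they match perfectly. The conflict does not depend on these figures. It needs correction because eligibility decides who is enrolled, and both the literal and the narrower reading of the criterion call for an amendment.

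**What to change.** Amend the section 4.2 criterion so that the psychiatric part is qualified by *other than anxiety and depressive disorders*. Keep the existing examples, the neurological part and the one-month medication exclusion, and add no new diagnostic categories, for which the protocol gives no basis.

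If the sponsor means to keep the exclusion in full, restrict the objectives in section 3, and the conclusions drawn from them, to anxiety and depressive symptoms in IBS patients without a psychiatric diagnosis. The objective on psychiatric comorbidity would then have to be dropped or reworded.

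The cost is an amendment approved by the Ethics Committee under section 10.1; it adds no procedures. Admitting these patients makes the IBS group more mixed. Patients who took anti-anxiety or antidepressant drugs within the past month stay excluded, so the score range is only partly restored.

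### Recent-medication and past-history exclusions bind only the IBS group, and a clean family history binds only controls, so IBS-versus-control contrasts can reflect unequal selection

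*Protocol*

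**What the plan says.** Section 4.2 of the protocol has one exclusion list, headed "Exclusion Criteria – IBS Group". It includes "History of antibiotics or probiotics use within the past month", a matching one-month exclusion for anxiety and depression medication, present or previous psychiatric or neurological disorder, gastrointestinal disease or surgery, and "Contraindications to 7.0T MRI".

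Controls have three inclusion lines and no exclusion list. The first repeats the handedness, age and education limits of the IBS group. The second is "All physiological indices within normal range, no disease manifestations". The third is "No family history of psychiatric or neurological disorders", which has no counterpart among the IBS criteria.

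The baseline visit in section 6.2, with MRI and stool and blood sampling, is not restricted by group, so controls are scanned and sampled. Section 8.1 names age, sex and BMI for adjustment; section 7.2 adds other confounders without naming them.

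**The concern.** A case-control contrast can be read as a disease effect only if both groups are screened for the same extraneous factors. Here two sets of factors are screened on one side only.

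By excluding IBS patients with recent antibiotic or probiotic use, the protocol treats that exposure as a contaminant of the microbiome and metabolome data. A healthy person who took either last week still meets the control criteria as written. So does a well person taking a psychotropic drug, or one with past gastrointestinal surgery or a resolved psychiatric episode.

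The family-history rule works the other way. Section 2.2 cites "shared genetic risk loci between IBS and anxiety/depression". Selecting controls for low familial liability, with no such condition on cases, can add a difference in mood and brain measures that would be credited to IBS. The Random Forest and ROC work in section 7.2 would carry the same distortion wherever it separates IBS from controls.

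**Working it through.** **Criteria side by side (section 4.2)**

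| Factor | IBS group | Controls |
|---|---|---|
| Antibiotics or probiotics, past month | excluded | not addressed |
| Psychotropic medication, past month | excluded | not addressed |
| Past psychiatric or neurological disorder | excluded | not addressed; overt present illness is covered |
| Past gastrointestinal surgery | excluded | not addressed |
| Overt gastrointestinal or organ disease, fever | excluded | reasonably covered by the general health line |
| 7T MRI contraindications | excluded | not in the criteria; Appendix C is an MRI safety form, not shown |
| Family history, psychiatric or neurological | no condition | must be absent |

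**Can the planned adjustment remove the imbalance?** Age, sex and BMI measure none of these factors. The other confounders in section 7.2 could include them, but only if they are collected. CRF Module 1 (section 6.1) lists neither family history nor recent antibiotic or probiotic use. Medication use appears only in Module 6, Follow-up, and the 3-month visit is for IBS patients only.

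**The plan's own figure, used as a scale.** Section 5 has δ = 0.5, σ = 1.0, two-sided α = 0.05 and 80% power. n = 2(1.96 + 0.8416)² × 1.0² / 0.5² = 62.8, so 63 per group. The t-distribution version gives 63.8, so 64, as stated. With 20% dropout, 64/0.8 = 80; the target is 100. Nothing below changes these numbers.

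**Possible size.** If a factor has prevalence p in one group, is screened out of the other, and shifts a measure by d SD, the spurious mean difference is p × d. The documents give neither p nor d, so these ranges are assumptions.

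- Family history, p = 10–30%, d = 0.2–0.5 SD: 0.10 × 0.2 = 0.02 to 0.30 × 0.5 = 0.15 SD.
- Antibiotics or probiotics in controls, p = 5–15%, d = 0.5–1.0 SD: 0.05 × 0.5 = 0.025 to 0.15 × 1.0 = 0.15 SD.

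Against δ = 0.5, the overall range is 0.02/0.5 = 4% to 0.15/0.5 = 30%.

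**What that does to a test.** The standard error of a difference is √(2/100) = 0.141 SD with 100 per group and √(2/80) = 0.158 SD with 80. The figures use the normal approximation.

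| Bias (SD) | Rejection rate, no true difference: 80 / 100 per group | Power if bias opposes a true 0.5 SD: 80 / 100 per group |
|---|---|---|
| 0 | 0.05 / 0.05 | 0.89 / 0.94 |
| 0.025 | 0.053 / 0.054 | 0.85 / 0.92 |
| 0.15 | 0.158 / 0.186 | 0.60 / 0.70 |

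At the upper end the bias is about one standard error (0.15/0.141 = 1.06). A larger sample does not shrink it; the false-positive rate rises from 0.158 to 0.186 between 80 and 100 per group.

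**The case against.** The strongest reply is that the text shows an opening for bias, not bias, and that much of the opening may be closed elsewhere. Several parts of it stand.

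- A reader might infer that the groups do differ. The documents support only that they can, because no exposure rate among controls is given.
- A reader might infer that every omics result is biased. The objectives in section 3 centre on anxiety and depression in IBS, and the 3-month repeat sampling is IBS only. Associations within the IBS group do not depend on who the controls are.
- A reader might infer that the diagnostic ROC is inflated. Section 7.2 does not say which groups the ROC separates, and section 3 seeks biomarkers for IBS with psychiatric comorbidity, which could be a within-IBS classification.
- A reader might infer that controls will be scanned without safety screening, or that the MRI criteria bias the contrasts. Appendix C lists a safety screening form and section 8.2 promises scanning SOPs; neither is limited by group in the text shown. No mechanism links implants or tattoos to an IBS contrast. This is a wording gap.
- Excluding IBS patients with psychiatric disorders plausibly lowers familial loading among cases, partly offsetting the family-history bias. Antibiotic or probiotic effects have no fixed direction and may mask differences as well as create them.
- The full CRF (Appendix A) and any SAP are not at hand and may collect or adjust for more.

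The last point does not dispose of the concern. Eligibility is fixed in the protocol, and a later analysis plan cannot change who was enrolled. The reliance in section 8.1 on strict adherence to the criteria would enforce the imbalance.

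**Conclusion.** The concern holds for IBS-versus-control contrasts. Unequal rules on recent antibiotics, probiotics and psychotropics, past psychiatric or neurological disorder and gastrointestinal surgery, together with a family-history rule for controls only, let selection produce or hide differences that would be read as effects of IBS. The adjustment named in the protocol does not address this.

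The size cannot be determined from the documents. The range of about 0.02 to 0.15 SD per factor rests wholly on the assumed prevalences and effects. Its lower end is negligible; its upper end would roughly triple the false-positive rate of a single comparison. The 0.5 SD used as a yardstick is not tied to any particular brain, mood or omics endpoint in section 5. The sample-size figure of 64 per group is unaffected.

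**What to change.** In section 4.2, apply the same exclusions for recent antibiotic, probiotic and psychotropic use, past psychiatric or neurological disorder, and gastrointestinal surgery to both groups. For consistency, head the 7T MRI contraindications as applying to all scanned subjects.

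Remove the family-history criterion for controls, or apply it to both groups. If it is removed, record family history at baseline in both groups and adjust for it. Recording it while keeping the controls-only rule does not work: it is then constant in controls, its effect can be estimated only from cases, and the adjusted comparison amounts to family-history-negative patients against controls.

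The study period began in April 2025, so some controls may already be enrolled. For them, collect recent medication and family history retrospectively, and run a sensitivity analysis that leaves out exposed controls. Recall will limit the quality of these data.

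The cost is an ethics amendment, one or two CRF items and a few more controls screened out.
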